4.2.3 Weekly GVHD Monitoring

GVHD scoring will be performed weekly for 8 weeks from study entry. Days 1, 28 and 56 (± 7 days) scoring must be performed by direct observation at the Transplant Center.

4.2.4 Serious Adverse Event (SAE) Reporting

Serious Adverse Events will be consistent with BMT CTN procedures (BMT CTN Administrative Manual of Procedures, Chapter 6) and reported through an expedited Adverse Event (AE) reporting system. Serious and unexpected Grades 3-5 adverse events should be reported within three working days. Deaths are to be reported within 24 hours. Other SAEs will be tracked periodically as defined in the Form Submission Schedule, and staged according to NCI Common Terminology Criteria for Adverse Events (CTCAE), Version 3.0.

The Data and Safety Monitoring Board will receive summary reports of all Grade 3-5 unexpected adverse experiences on an annual basis.

Table 4.2.2 REQUIRED ASSESSMENTS

	(Day 0)	Days Post Randomization											
	Baseline	7	14	21	28	35	42	49	56	90	120	180	270
Suggested biopsy of involved tissue (+ extra skin biopsy Days 1 & 28 ¹)	X				X								
History and physical exam	X												
Pregnancy test (if applicable)	X												
Karnofsky/Lansky performance status					X					X		X	X
Acute GVHD evaluation	X	X	X	X	X	X	X	X	X	X	X	X	X
Chronic GVHD evaluation										X	X	X	X
CBC with differential, platelet count	X	X	X	X	X	X	X	X	X				
Basic chemistry (creatinine)	X	X	X	X	X	X ²							
Liver function tests (alkaline phosphatase, bilirubin, AST, ALT)	X	X	X	X	X	X	X	X	X	X	X	X	X
Toxicity evaluation		X	X	X	X	X	X	X	X				
Steroid dose		X	X	X	X	X	X	X	X	X	X	X	X
Tacrolimus/cyclosporine levels	X	X	X	X	X								
MMF levels (see Appendix C-5 ¹)		X	X										
Blood and serum for ancillary laboratory studies (see Appendix C ¹)	X		X		X					X			

¹ Research procedures beyond that required for usual care.² Recommended

CHAPTER 5

5 STATISTICAL CONSIDERATIONS

5.1 Study Design Synopsis

This study is a multi-center, randomized two-stage Phase II trial designed to evaluate several frontline treatments for acute GVHD. After 20 patients per treatment are evaluable (stage I), a stopping rule for lack of efficacy will be applied, so that future patients may be randomized to the most promising treatments. The remaining patients will be randomized in stage II to the treatments passing through stage I, to a maximum of 65 patients per arm or 180 patients total.

5.2 Accrual

It is estimated that nine months of accrual, or approximately 20 patients per month, will be necessary to enroll the targeted sample size. Only Core Centers will enroll patients on this study.

5.3 Randomization

Randomization will occur separately in two strata. Stratum 1 consists of patients who had received MMF previously as GVHD prophylaxis and are not eligible to receive MMF again as GVHD treatment, while stratum 2 consists of patients who did not receive MMF previously as GVHD prophylaxis. Patients in stratum 1 will be randomized in equal proportions to the other three treatment arms. Patients in stratum 2 will be randomized in unequal proportions to all four arms (initially 40% to MMF and 20% to each of the other three arms). This unequal allocation was chosen to target approximately equal sample sizes per arm (45) by the end of the study, assuming 33% of patients will belong to stratum 1. Randomization in each stratum will occur using two sets of permuted blocks of varying sizes. One set of permuted blocks will determine MMF vs. not MMF for patients in stratum 2, while the other set will determine which of the other three arms the patient is assigned to. After 80 patients have been enrolled and followed up for the primary endpoint, two things will be assessed. First a stopping rule will be applied as described below to determine whether any of the arms should be closed for lack of efficacy. Second, the proportion of patients entering stratum 1 will be assessed. If the MMF treatment arm is closed for lack of efficacy, then we will revert to equal randomization for any remaining treatment arms. Otherwise, based on the number of non-MMF arms remaining (i.e. not closed for lack of efficacy) and the proportion of patients entering stratum 1, we will adjust the allocation probability P to MMF treatment in stratum 2 according to the following formula:

$$P = (k * i + 3 * (180 - i) - 4 * k * y) / (3 * (k + 1) * (180 - i) * (1 - r)),$$

where r=observed percent of MMF prophylaxis use so far, i=80 is the number accrued, k is the number of non-MMF treatment arms remaining, and y is the number assigned to MMF treatment. This formula is obtained by setting the expected final number of patients assuming allocation of P in stratum 2 to MMF treatment equal to the expected final number of patients in

each of the other treatment arms. Some examples of the new allocation rates are given in the table below, as a function of the observed MMF prophylaxis rate and the number of remaining arms. Also given are the expected sample sizes after 80 patients and after 180 patients in both the MMF arm and a representative non-MMF arm.

Evaluated at		After 80 Patients		New P	After 180 Patients	
MMF Rate, r	# of non-MMF arms remaining, k	# MMF	# other trt		# MMF	# other trt
0.2	3	26	18	0.243	45	45
0.2	2	26	18	0.354	54	54
0.2	1	26	18	0.578	65	65
0.33	3	21	20	0.352	45	45
0.33	2	21	20	0.478	53	53
0.33	1	21	20	0.732	65	65
0.45	3	18	21	0.498	45	45
0.45	2	18	21	0.645	53	53
0.45	1	18	21	0.938	65	65
0.5	3	16	21	0.580	45	45
0.5	2	16	21	0.738	53	53
0.5	1	16	21	1.000	60	65

5.4 Primary Endpoint

The primary endpoint for the trial is the proportion of complete response to acute GVHD therapy at Day 28.

5.5 Primary Hypothesis

Each arm will be compared to the historical rate of 35% CR at Day 28 of therapy. This will be done by computing a “Bayesian posterior probability of efficacy,” i.e., the Bayesian posterior probability that the response rate is > 35%, using a Beta (3.5, 6.5) prior distribution. This prior has a mean of 35% and a “weight” of 10 patients. If this posterior probability of efficacy is > 90%, the treatment is considered a candidate for further investigation based on the primary endpoint. No statistical comparisons between the arms will be performed: the purpose of the trial is only to identify treatments for further investigation through comparisons to a historical control of corticosteroids alone and is underpowered for comparisons among the arms.

5.6 Study Design

Stage I: Randomize patients in two strata as described above until 80 patients are evaluable for the primary endpoint. After 80 patients are evaluable, apply the following stopping rule for lack of efficacy: if the Bayesian posterior probability of efficacy for a particular arm is < 20%, close the arm to further accrual. This Bayesian stopping rule is equivalent to stopping if the number of patients alive in CR at Day 28 is less than or equal to 4 out of 20.

Stage II: Continue randomizing patients after modifying the randomization scheme as described above. If the MMF treatment arm is dropped for lack of efficacy, then the randomization will be done equally among all remaining treatment arms. If not, then the randomization probabilities will be recomputed according to the rate of MMF prophylaxis use in the first 80 patients as well as the number of remaining non-MMF treatment arms that passed successfully through stage I. This randomization will be done up until a maximum of 65 per group or 180 patients have been accrued. At the end of the study, a treatment identifying a good candidate will be based on the primary endpoint if the Bayesian posterior probability of efficacy is $> 90\%$.

This Bayesian rule corresponds to a cutoff in terms of numbers of patients alive in CR at Day 28, which depends on the final enrolled sample size and therefore the number of treatment arms passing through stage I. Sample cutoffs are given in Table 5.6 below.

Table 5.6
CUTOFFS FOR PATIENTS ALIVE IN CR AT DAY 28

Number of Treatments Passing through Stage I	Final n per Treatment Group	Declare Treatment a Good Candidate if # of CRs is $\geq x$
1	65	29
2	65	29
3	52	24
4	45	21

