Treatment Description: The treatment schedules are as follows: **Etanercept** [25 mg subcutaneously twice weekly for up to 4 weeks; discontinue if in CR by 4 weeks]. Mycophenolate mofetil (**MMF**) [20 mg/kg (maximum 1 gm) PO or IV BID; continue through prednisone taper, then taper MMF over 4 weeks]. Denileukin Diftitox (**ONTAK®**) [9 mcg/kg IV Days 1, 3, 5, 15, 17, 19]. **Pentostatin** [1.5 mg/m² daily for 3 days; Days 1-3 and repeat Days 15-17].

All patients will receive methylprednisolone 2 mg/kg/day IV (or prednisone 2.5 mg/kg/day PO) divided in 2-3 daily doses for at least 7 days. Prednisone may be tapered as tolerated to no less than 0.75 mg/kg/day (methylprednisolone 0.6 mg/kg/day) at Day 28 of therapy. If not in CR at Day 28, patients will be followed for study endpoints, but assigned therapy can be continued or changed per institutional guidelines.

In addition to prescribed study drug plus corticosteroids, all patients should receive transfusion support per institutional practice; anti-infective prophylaxis directed towards CMV, gram positive (encapsulated) bacteria, pneumocystis carinii and fungal infections

[figure not shown]
Weekly GVHD organ stage scores, overall clinical grade, biopsy information for GVHD and relevant differential diagnosis will be recorded and reported to the BMT CTN Data Coordinating Center (DCC).

Accrual Objective: A maximum of 180 patients, but at most 65 per arm, will be randomized to one of the four treatment arms. After 80 patients are evaluable for the primary endpoint, if in any experimental arm, observed responses suggest a posterior probability > 85% that an arm will have a true CR < 35%, enrollment to the arm will cease and the arm will be excluded from further consideration due to lack of evidence for efficacy.

Accrual Period: The estimated accrual period is 12 months.

Study Duration: Patients will be followed for 9 months following initiation of therapy.

STUDY DESIGN SCHEMATIC

* Steroids = 2.5 mg/kg prednisone/day PO or IV equivalent in methylprednisolone (2 mg/kg) divided 2-3 times daily

Primary Endpoint:
Proportion of CR at Day 28 of therapy.

STUDY SCHEMA

Aim: To determine if any of four new agents, given in addition to corticosteroids as initial therapy for acute GVHD improves response rate and overall clinical outcome.

Inclusion Criteria	Exclusion Criteria

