5.8 Stopping Guidelines

At the end of stage I, lack of efficacy stopping guidelines will be implemented separately for each arm. If the Bayesian posterior probability of efficacy for a particular arm is $< 20\%$, it will be recommended that the arm be closed to further accrual. For lack of efficacy, an arm will be closed if the posterior probability is $\leq 20\%$ that the CR rate at Day 28 is greater than 35%. This is equivalent to stopping for lack of efficacy if 4 or fewer of the first 20 patients are CRs. Once the stopping criteria have been met for a particular arm, no more patients will be randomized to that arm.

After 20 patients have been accrued, this stopping rule for lack of efficacy results in the following stopping probabilities as a function of the true CR rate.

Table 5.8
STOPPING GUIDELINES

N Evaluable	Stop if # of CRs are	Probability of Stopping for Lack of Efficacy			
		CR=15%	CR=25%	CR=35%	CR=45%
20	≤ 4	83%	42%	12%	2%

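### The stage I futility threshold is a 15% posterior probability of efficacy in the synopsis but 20% in Sections 5.6 and 5.8, and the two decide differently at arm sizes the plan expects

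*Combined protocol and SAP*

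**What the plan says.** The synopsis, under Accrual Objective, acts after 80 patients are evaluable. It stops enrollment to an arm "if in any experimental arm, observed responses suggest a posterior probability > 85% that an arm will have a true CR < 35" per cent.

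Section 5.6 (Stage I) sets a different limit at the same look: "if the Bayesian posterior probability of efficacy for a particular arm is < 20%, close the arm to further accrual". It then gives a count: "This Bayesian stopping rule is equivalent to stopping if the number of patients alive in CR at Day 28" is at most 4 out of 20. Section 5.8 repeats the 20% limit, says "At the end of stage I, lack of efficacy stopping guidelines will be implemented separately for each arm", and adds "This is equivalent to stopping for lack of efficacy if 4 or fewer of the first 20 patients are CRs".

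Section 5.5 defines the probability of efficacy as the posterior probability that the response rate exceeds 35%, "using a Beta (3.5, 6.5) prior distribution".

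Section 5.3 fixes the timing by the total: "After 80 patients have been enrolled and followed up for the primary endpoint, two things will be assessed". It introduces its allocation table with "Also given are the expected sample sizes after 80 patients and after 180 patients". The sizes listed at 80 patients are:

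| MMF prophylaxis rate r | MMF arm | Each other arm |
|---|---|---|
| 0.20 | 26 | 18 |
| 0.33 (planning value) | 21 | 20 |
| 0.45 | 18 | 21 |
| 0.50 | 16 | 21 |

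**The concern.** A posterior probability above 85% that CR is below 35% is the same as a posterior probability of efficacy below 15%. The synopsis and the statistical chapter therefore state two different thresholds for the only lack-of-efficacy look.

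That look decides which agents stay open. Through the number of open arms it also sets the stage II allocation (Section 5.3) and the final sample size per arm (Table 5.6). If the thresholds led to the same counts, the mismatch would be a slip of wording. If they part at arm sizes the trial is likely to have, the monitoring board could face data that close an arm under one part of the document and keep it open under another. The choice would then be made with the results in view.

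**Working it through.** **Inputs.** Prior Beta(3.5, 6.5) and reference rate 35% (Section 5.5); thresholds of 15% (synopsis) and 20% (Sections 5.6 and 5.8); expected arm sizes at 80 patients (Section 5.3). The synopsis names no prior, so the Section 5.5 prior, the only one given, is used for both rules.

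**Formulas.** With x CRs among n patients, the posterior is Beta(3.5 + x, 6.5 + n − x). The cutoff c is the largest x for which P(CR > 0.35) is below the threshold. The chance of closing at true rate p is the binomial probability P(X ≤ c | n, p).

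**The plan's own figures.** At n = 20 the posterior probability of efficacy is 10.8% with 4 CRs and 20.3% with 5. Both thresholds therefore give c = 4. The closing probabilities at true CR 15, 25, 35 and 45% are 83.0, 41.5, 11.8 and 1.9%, which match Table 5.8 (83, 42, 12 and 2%). The printed count is right at n = 20, but it cannot show which threshold was meant.

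**Arm sizes.** Under the initial 40% allocation in stratum 2, the expected MMF size is 80 × (1 − r) × 0.4, and each other arm gets one third of the rest. At r = 0.33 this is 80 × 0.67 × 0.4 = 21.4 and (80 − 21.4)/3 = 19.5, printed as 21 and 20. The other rows reproduce in the same way.

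**Cutoffs at the printed sizes.**

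| n | Close if CRs ≤ (20% rule) | Close if CRs ≤ (15% rule) | Posterior at the disputed count |
|---|---|---|---|
| 16 | 3 | 3 | – |
| 18 | 4 | 3 | 4/18: 16.2% |
| 20 | 4 | 4 | – |
| 21 | 5 | 4 | 5/21: 17.0% |
| 26 | 6 | 6 | – |

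Over n = 14 to 29 the cutoffs also differ at 14, 15, 17, 24, 27 and 28.

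**Chance of closing where the rules part.**

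| True CR | n = 18: 15% rule / 20% rule | n = 21: 15% rule / 20% rule |
|---|---|---|
| 25% | 30.6% / 51.9% | 36.7% / 56.7% |
| 35% | 7.8% / 18.9% | 9.2% / 20.1% |
| 45% | 1.2% / 4.1% | 1.3% / 3.9% |
| 50% | 0.4% / 1.5% | 0.4% / 1.3% |

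**Chance that at least one of the four arms is decided differently.** This was simulated with 80 patients. Block sizes are not given in the plan. Blocks of 5/10 (MMF or not) and 3/6 (the other three arms, shared across strata) were assumed.

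| True CR, all arms | r = 0.33 | r = 0.50 | r = 0.20 |
|---|---|---|---|
| 25% | 15% | 34% | 43% |
| 35% | 8% | 20% | 26% |
| 45% | 2% | 5% | 7% |
| 50% | 0.9% | 2.2% | 3.2% |

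With blocks of 10/20 and 6/12, the 35% row becomes 10, 17 and 25%.

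**Effect on the final decision.** With final n fixed and the Table 5.6 cutoffs, an exact two-stage calculation moves the good-candidate probability by at most 0.5 points at stage I sizes 18 and 21, and by at most 1.1 points over 14 to 29. With final n depending on the arms left open (simulated, mortality rule ignored), the largest shift is about 2 points: at r = 0.20 with only MMF at 50%, 75.0% under the 15% rule against 77.1% under the 20% rule. At r = 0.33 the shift is under 0.5 points. There the 20% rule gives 7.5, 50.0, 75.4 and 72.2%, where Table 5.7 prints 7, 49, 75 and 72%.

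**A non-issue.** Section 5.8 writes the limit once as below 20% and once as at or below 20%. For n = 10 to 32 no posterior lies closer to 20% than 0.3 points (5/20), so this changes no decision.

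**The case against.** The strongest reply is that the operative rule is hardly in doubt. Chapter 5 gives the prior, the 20% limit in two sections, the count and Table 5.8. The outlier is one synopsis clause. That supports 20% as the likely intention, but no text says Chapter 5 prevails, and the synopsis states a rule that could be applied as written.

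Second, Section 5.8 speaks of the first 20 patients. Read literally, an arm of 21 is judged on its first 20, where the thresholds agree. The disagreement at n = 21 does depend on not reading it that way. But that reading cannot be applied to an arm of 16 or 18, and it fits poorly with a look triggered by 80 patients in total.

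Third, the Section 5.3 table gives examples over several prophylaxis rates, and only 33% is the planning assumption. At that rate only the MMF arm, at 21, has a discordant expected size, and the rules agree at 19, 20 and 22. Size 18 is expected only at r = 0.20 (other arms) or r = 0.45 (MMF). This stands and limits the size of the problem.

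Fourth, final power barely moves, and Section 5.8 words closure partly as a recommendation. Both are true. Neither settles which threshold the recommendation should use.

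**Conclusion.** The concern holds. The plan gives two thresholds for one decision, and they disagree by one CR at arm sizes 18 and 21, both printed as expected. Size 21 is the MMF arm at the planned prophylaxis rate. In each disputed case (4/18, 5/21) the arm closes under Sections 5.6 and 5.8 and stays open under the synopsis.

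At these sizes the 20% rule roughly doubles the chance of closing an arm whose true CR rate equals the 35% reference. It rarely matters for an arm at 50%. In the planned case with all arms at 35%, the chance that some arm is decided differently is about 8 to 10%. This rests on the Section 5.5 prior applying to both rules, on each arm being judged on all its evaluable patients at the look, and, for the trial-level figures, on the assumed block sizes.

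The count of 4 out of 20 and Table 5.8 are correct at n = 20. The fault is an ambiguous pre-specified rule, which should be fixed; it is not a loss of power.

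**What to change.** Bring the synopsis and Sections 5.6 and 5.8 to one threshold: the statistical chapter's 20%, unless 15% was intended. State that it applies to all evaluable patients on each arm when 80 are evaluable in total. Align with that trigger the wording in Section 5.1 (20 patients per treatment) and Section 5.8 (first 20). Say that 4 out of 20 and Table 5.8 are the n = 20 case, and add cutoffs by actual arm size, with their closing probabilities:

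| Close if CRs ≤ | 20% rule: n | 15% rule: n |
|---|---|---|
| 2 | – | 14–15 |
| 3 | 14–16 | 16–18 |
| 4 | 17–20 | 19–21 |
| 5 | 21–23 | 22–24 |
| 6 | 24–26 | 25–28 |
| 7 | 27–29 | 29 |

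Only the column for the chosen threshold should be printed.

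The cost is a one-line correction to the synopsis, minor wording and one small table, with no extra patients. Keeping 20% changes no threshold in Chapter 5. The printed closing probability over n = 14 to 29 would then run from 11.8% to 23.5% for an arm at 35% and from 40.5% to 64.3% for an arm at 25%, which the 20% rule already implies. Choosing 15% gives 6.2% to 17.3% and 23.6% to 56.1%, so more poor arms stay open at the sizes where the cutoffs differ.

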5.7 Power and Operating Characteristics of Study Design

This design, including the stopping rules for lack of efficacy as well as stopping for mortality discussed in Section 5.8, was simulated for several configurations of true success rates, which represent improvements over the historical rate of 0%, 10%, 15%, and 20%. Table 5.7 below gives the configurations of true CR rates considered, with bold entries denoting effective treatments relative to the historical control rate of 35%. Note that because there are multiple decisions being performed on the various treatments, there is no simple definition of power or type I error. Therefore, for each configuration of success rates, several measures of power and type I error are presented which are appropriate for a design with multiple arms. Also note that these operating characteristics apply for the situation when the true proportion r in stratum 2 is 33%. Deviations from this will have minimal impact on the operating characteristics because the final sample sizes are similar regardless of r .

First we report the marginal probability of identifying treatment arm 1 as a good candidate. This can be interpreted as the power for arm 1 individually, if arm 1 is effective, and the type I error rate for arm 1 individually if arm 1 is not effective. Next we report the probability that all effective treatments are identified as good candidates and no ineffective treatments are identified, which can be interpreted as a “perfect” decision on all treatments. Third, we present the probability that at least one effective treatment is identified as a good candidate and no ineffective treatments are identified. This can be interpreted as a “perfect” decision on the ineffective treatments and a “good” decision on the effective treatments (i.e. we correctly

identified at least one good candidate). Finally, we present the probability that at least one ineffective treatment is identified as a good candidate, while none of the effective treatments are identified. This can be interpreted as a type I error and is an undesirable result. Results are based on 10000 simulated datasets for each scenario. Note that this two-stage design has approximately 75% marginal probability or power to detect an improvement of 15% in the CR rate over the historical control rate, and more than 90% marginal power to detect a 20% improvement. Also, if there are two or more effective treatments with 50% CR rates, the design has at least 80% power to identify at least one of them as a good candidate while not identifying any ineffective treatments.

Table 5.7
POWER AND OPERATING CHARACTERISTICS

True CR Rates (Effective arms denoted in bold)					Probability of Identifying as Good Candidates:			
Arm 1	Arm 2	Arm 3	Arm 4	Arm 1	All effective treatments and no ineffective treatments	At least one effective treatment and no ineffective treatments	No effective treatments and at least one ineffective treatment	
0.35	0.35	0.35	0.35	7%	-	-	27%	
0.45	0.35	0.35	0.35	49%	40%	40%	10%	
0.50	0.35	0.35	0.35	75%	59%	59%	5%	
0.55	0.35	0.35	0.35	91%	72%	72%	2%	
0.50	0.50	0.35	0.35	74%	47%	80%	1%	
0.50	0.50	0.50	0.35	72%	35%	91%	0%	
0.50	0.50	0.50	0.50	72%	27%	99%	-	

Frequentist confidence intervals (CI) will also be constructed for the CR rate at Day 28. For a treatment which is declared a good candidate ($\geq 29/65$ or $24/52$ or $21/45$ CRs), a 90% CI will have a lower bound of at least 34% and a 95% CI will have a lower bound of at least 32%.

